6.1.2 Study Workflow

Study flow is shown in Figure 1. All available Xpert MTB/RIF TB-positive samples will be tested in this study (i.e. consecutive patient samples) until sample size targets are met. All molecular assays will be performed in accordance with SOPs provided by the manufacturers. Specimen handling and processing by routine tests will be carried out according to NTP local policies and standards.

Samples will first be tested by Xpert MTB/RIF or Ultra, as part of routine diagnostic procedures. This Xpert MTB/RIF step will act as a screening tool for trial enrolment. Participants testing positive for MTB by Xpert MTB/RIF will be asked to volunteer for the Xpert MTB/XDR trial. This (testing of specimens from TB-positive samples) is in line with the intended use of the XDR assay as an add-on test to the Xpert MTB/RIF assay.

[figure not shown]
A staged enrolment will proceed: Stage 1 will enrol 360 MTB-positive participants, irrespective of RIF resistance/sensitivity. Once enrolment is complete, Stage 2 will enrol 400 MTB-positive RIF-resistant participants (see section 9.1 and Appendix 4: Sample Requirement to Achieve Target Sample Size). This staging is designed to better evaluate Xpert MTB/XDR sensitivity for second-line resistance detection.

In order to efficiently assess the diagnostic performance of the Xpert MTB/XDR assay, participants will be asked to provide ≥ 3 ml of sputum (either a single sputum or two consecutively collected and pooled sputa). Samples will be homogenized and split for testing.

The Xpert MTB/XDR assay and acid-fast bacilli smear will be performed on the direct sample. 2ml of sputum will be decontaminated and used for MGIT and LJ culture.

Following direct testing, phenotypic MGIT DST will be performed for all culture-positive samples for INH, RIF, fluoroquinolone (moxifloxacin and levofloxacin), AMK, ETH (ethionamide), KAN and CAP. Cultured samples will also undergo subsequent molecular testing by LPA and targeted NGS of relevant gene regions (*katG*, *inhA*, *fabG1*, *ahpC*, *gyrA*, *gyrB*, *rrs*, and *eis*) and another Xpert MTB/XDR assay. NGS will be performed from the culture isolate to obtain sequencing reads of high quality.

Figure 1. Phase II sample flow

≥ 3ml of sputum is required for the trial. This can be achieved through an individual sputum or pooling of serially collected sputa, homogenized with glass beads.

All diagnostic test results (smear, Xpert MTB/XDR on direct sample, MGIT, LJ, Xpert MTB/XDR on culture isolate, MTBDR*plus*, MTBDR*sl*, DST and NGS results) will be recorded by the laboratory technicians for each site on the laboratory CRF.

7 Specimen Collection, Handling, Transport and Storage

Clinical (sputum) samples from enrolled patients will be used in this study. Patients will be asked to provide up to two sputum samples for testing after providing informed consent for the study. Sputum samples from the same patient will be pooled and used directly for acid-fast bacilli smear, Xpert MTB/XDR and MGIT and LJ culture.

Appropriate laboratory staff at each site reference laboratory are responsible for receiving the samples, storing the samples and conducting all testing in line with BSL3 requirements. All leftover samples must be stored until study conclusion and completion of all analyses, in case any additional or repeat testing is requested by the sponsor.

7.1 Reference Standard Test and Index Test Procedures

A composite reference standard of phenotypic DST and NGS will be used for resistance detection to ensure high confidence in the reference standard for this study. Phenotypic MGIT DST and targeted NGS will be performed on the culture isolate for each clinical sample. MGIT DST will be done on site to determine culture drug-susceptibility to INH, ETH, moxifloxacin, levofloxacin, AMK, KAN and CAP at the revised WHO critical concentrations¹⁵. Targeted NGS of the gene regions included in the Xpert MTB/XDR assay will be performed on DNA extracted from the cultured sample, which will be sent to a SNRL for NGS, or sequenced locally using primers specific for the gene regions included in the assay. The output for both phenotypic DST and NGS results are automated, and require no manual operator interpretation. Testing results, when obtained, will be input onto the laboratory CRF.

The index test will be performed on both the direct clinical sample as well as the culture isolate, to ensure high Xpert MTB/XDR diagnostic performance direct from sputum and to provide a basis for comparison if any discordants are seen between the initial Xpert MTB/XDR result and the phenotypic DST and additional molecular test results (NGS and LPA). The output for the Xpert MTB/XDR assay is automated and does not require manual interpretation. As with the reference test, all Xpert test results will be noted on the laboratory CRF.

7.2 Genetics

No patient genetic information will be collected, analysed or recorded in this study. The proposed genetic sequencing and molecular analysis protocols use only TB pathogen-specific sequences and will be limited to analysis of *M. tuberculosis* bacteria genomes.

7.3 Biomarkers

Biomarkers are not evaluated in this study.

8 Safety and Incident Reporting

The definitions of an adverse event (AE) and serious adverse event (SAE) can be found in Appendix 1: Safety Definitions and Reporting.

AE will be reported by the participant spontaneously (or, when appropriate, by a caregiver, surrogate, or the participant's legally authorized representative).

The investigator and any qualified designees are responsible for detecting, documenting, and recording events that meet the definition of an AE or SAE and remain responsible for following up AEs that are serious, considered related to the study intervention or study procedures, or that caused the operator to discontinue

use of the Xpert MTB/XDR assay or participants to discontinue their participation in the Xpert/MTB XDR Clinical Evaluation.

8.1.1 Time Period for Collecting SAE Information

All SAEs will be collected from the signing of the informed consent form (ICF) OR start of Xpert MTB/XDR testing until the end of the Xpert MTB/XDR Clinical Evaluation at the time points specified in the SOP.

All SAEs will be recorded and reported to the sponsor or designee within 24 hours, as indicated in Appendix 2: Incident Definition and Reporting. The investigator will submit any updated SAE data to the sponsor within 24 hours of it being available.

Investigators are not obligated to actively seek SAEs after conclusion of the study participation. However, if the investigator learns of any SAE, including a death, at any time after a participant has been discharged from the study, or the IVD operators have completed IVD testing, and he/she considers the event to be reasonably related to the study intervention or study participation, the investigator must promptly notify the sponsor.

The method of recording, evaluating, and assessing causality of the SAE and the procedures for completing and transmitting SAE reports are provided in Appendix 1: Safety Definitions and Reporting.

8.1.2 Reporting and Follow up of SAEs

All SAEs will be followed until resolution, stabilization, the event is otherwise explained, or the participant is lost to follow-up (as defined in Section **Error! Reference source not found.**). Further information on follow-up procedures is given in Appendix 2: Incident Definition and Reporting)

8.1.3 Regulatory Reporting Requirements for SAEs

Prompt notification by the investigator to the sponsor of a SAE is essential so that legal obligations and ethical responsibilities towards the safety of participants and the safety of a study intervention under clinical investigation are met.

The sponsor has a legal responsibility to notify both the local regulatory authority and other regulatory agencies about the safety of a study intervention under clinical investigation. The sponsor will comply with country-specific regulatory requirements relating to safety reporting to the regulatory authority, IRB/IEC, and investigators.

An investigator who receives an investigator safety report describing a SAE or other specific safety information (e.g., summary or listing of SAEs) from the sponsor will review and then file it in the Investigator Site File (ISF) and will notify the IRB/IEC, if appropriate according to local requirements.

8.1.4 IVD Incidents (including Malfunctions)

IVDs are being provided for use in this study for investigative purposes. In order to fulfil regulatory reporting obligations worldwide, the investigator is responsible for the detection and documentation of events meeting the definitions of incident or malfunction that occur during the study with such devices.

The definition of an IVD Incident can be found in Appendix 2: Incident Definition and Reporting.

NOTE: Incidents fulfilling the definition of an AE/SAE will also follow the processes outlined above and in Appendix 1: Safety Definitions and Reporting of the protocol.

8.1.5 Time Period for Detecting IVD Incidents

IVD incidents or malfunctions of the device that result in an incident will be detected, documented, and reported during all periods of the study in which the IVD is used.

If the investigator learns of any incident at any time after a participant has been discharged from the study, and such incident is considered reasonably related to a IVD provided for the study, the investigator will promptly notify the sponsor.

The method of documenting IVD Incidents is provided in Appendix 2.

8.1.6 Follow-up of IVD Incidents

All IVD incidents involving an AE will be followed and reported in the same manner as other AEs (see Section 8.1.2). This applies to all participants, including those who discontinue study intervention.

The investigator is responsible for ensuring that follow-up includes any supplemental investigations as indicated to elucidate the nature and/or causality of the incident.

New or updated information will be recorded on the originally completed form with all changes signed and dated by the investigator.

8.1.7 Reporting of IVD Incidents to Sponsor

IVD incidents will be reported to the sponsor within 24 hours after the investigator determines that the event meets the protocol definition of a IVD incident.

The Medical Device Incident Report Form will be sent to the sponsor by email. If email is unavailable, then the form should be faxed to the sponsor at [contact].

The Trial Manager will be the contact for the receipt of IVD and SAE.

8.1.8 Regulatory Reporting Requirements for Medical Device Incidents

The investigator will promptly report all incidents occurring with any IVD provided for use in the study in order for the sponsor to fulfil the legal responsibility to notify appropriate regulatory authorities and other entities about certain safety information relating to medical devices being used in clinical studies.

The investigator, or responsible person according to local requirements (e.g., the head of the medical institution), will comply with the applicable local regulatory requirements relating to the reporting of incidents to the IRB/IEC.

9 Statistical Considerations

A detailed statistical analysis plan will be prepared separately and only some key elements are presented here.

9.1 Sample Size Determination

To achieve the targeted precision for accuracy estimates, we estimate that 760 samples be tested for this study, with a final 284 MTB-positive and an additional 316 RIF-resistant samples tested by Xpert MTB/XDR and all reference standards and comparators (assumptions provided in Appendix 4), i.e. a total of 600 specimen results available for analysis. The desired precision for the accuracy estimates was chosen to achieve high confidence in the estimates for Xpert MTB/XDR resistance detection when considering evidence from both the 'external laboratory validation' (phase I) and the clinical trial (phase II). Sample size is detailed below in Table 2.

Table 2. Sample size

		Clinical trial (TB samples)		
		n	Point estimate (95%CI) *	Total width of CI *
INH	Sensitivity	395	90% (86, 93)	7%
	Specificity	205	98% (95, 99)	4%
FQs	Sensitivity	93	90% (82, 95)	13%
	Specificity	507	98% (96, 99)	3%

AMK	Sensitivity	34	90% (74, 97)	23%
	Specificity	566	98% (96, 99)	3%
KAN	Sensitivity	71	90% (80, 96)	16%
	Specificity	529	98% (96, 99)	3%
CAP	Sensitivity	34	90% (74, 97)	23%
	Specificity	566	98% (96, 99)	3%

* 95%CI based on Wilson's score method (as recommended by Newcombe et al. as well as CLSI/FDA) using continuity correction.

9.2 Statistical Analysis Plan

The statistical analysis plan (SAP) will be developed and finalized before database lock and will describe the samples to be included in the analyses and procedures for accounting for missing, unused, and spurious data. This section is a summary of the planned statistical analyses of the primary and secondary endpoints.

Primary analyses of outcome data will be done using the composite reference standard. Primary analyses will be focused on estimating accuracy (clinical sensitivity and specificity) for INH and second-line drug resistance detection:

- **Clinical Sensitivity:** proportion positive by composite reference standard (phenotypic DST and NGS) that are detected as positive by index test (Xpert MTB/XDR)
- **Clinical Specificity:** proportion negative by composite reference standard (phenotypic DST and NGS) that are detected as negative by index test (Xpert MTB/XDR)

For simple proportions (sensitivity and specificity), 95% confidence intervals will be computed using the Wilson score method. Primary diagnostic accuracy analyses will be carried out across all study sites. All TB samples that generate both Xpert MTB/XDR and composite reference standard results will contribute to the analysis of the performance characteristics for INH- and second-line resistance detection. If discordances are observed between the Xpert MTB/XDR results from testing sputa and the culture isolate, results from the culture isolate will be considered in these analyses.

Primary analyses will also evaluate assay operational characteristics, which will be captured through direct observation and user-appraisal questionnaires. Primary assessments of Xpert MTB/XDR operational characteristics will evaluate assay characteristics compared to Hain MTBDR*plus/sl* assays, including:

- Time to first result
- Ease of use
- Failure and invalid rate

These assessments of Xpert and LPA characteristics will be descriptive, and any differences will be further explored by sample type (i.e. smear- and culture-result, patient HIV- and treatment statuses, etc.). Assessments of platform operational characteristics will be based upon information gathered during the clinical study, as well as information provided by the manufacturers.

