5.3.2 Index Test

The Xpert MTB/XDR assay detects Mtb mutations associated with INH, ETH and second-line drug resistance direct from sputum. In line with this intended use, clinical samples will be directly tested by the Xpert MTB/XDR assay. However, the assay will also be used to test the culture isolate. This additional Xpert MTB/XDR assay testing will allow for a comparison of performance and non-determinant rates between testing directly from the sample and testing from the culture isolate. It will also support resolution of potential discordant LPA and NGS results from the initial Xpert MTB/XDR test result, as these tests will also be performed from the culture isolate (discordance may arise as a result of infections with a mix of different strains, with only one strain being grown out in culture). Furthermore, as all assays will be performed on the same culture, there is also no risk of any assay being tested on a different quality sample.

Review bias will be avoided in this study as the index test requires no manual interpretation by the operator. All results are automatically generated by the GeneXpert instrument and will be directly recorded by the operator on the laboratory case report form (CRF).

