4.2 Analysis of the primary outcome(s)

The primary objectives 1.1, 1.2 and 1.3 will be analysed with the methodology described in section 4.1.

Outcome 1.1

Estimates of sensitivity and specificity of Xpert MTB/XDR will be calculated, for INH and ETH resistance detection with phenotypic DST and *katG*, *fabG1*, *ahpC* and *inhA* sequencing results as a composite reference standard (see Appendix). This outcome will be evaluated on the PP population.

Outcome 1.2

Estimates of sensitivity and specificity of Xpert MTB/XDR will be calculated, for fluoroquinolone resistance detection, with phenotypic DST and *gyrA* and *gyrB* sequencing results as a composite reference standard (see Appendix). This outcome will be evaluated on the PP population.

Outcome 1.3

Estimates of sensitivity and specificity of Xpert MTB/XDR will be calculated, for second-line injectable resistance detection, with phenotypic DST and *rrs* and *eis* sequencing results as a composite reference standard (see Appendix). This outcome will be evaluated on the PP population.

Outcome 1.4

Assess Xpert MTB/XDR operational aspects and ease of use, including Xpert MTB/XDR non-determinant rates.

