4.3 Analysis of the secondary outcome(s)

Outcome 2.1

Direct performance versus performance on cultured samples:

- Estimates of diagnostic performance for each drug split by specimen type used for Xpert MTB/XDR (sputum or culture)

Performance between sites:

- Estimates of diagnostic performance for each individual site (India-NITRD, India-Hinduja, Moldova, and South Africa)

Performance by smear result:

- Estimates of diagnostic performance by smear gradation (smear negative, scanty, +1, +2, +3)

Performance by gene target

- Count of the number of times resistance was detected by the assay when a mutation was present in the gene region (NGS) for each gene target (*katG*, *inhA*, *ahpC*, *fabG1*, *gyrA*, *gyrB*, *rrs*, *eis*)

Performance compared to Hain MTBDR*plus/sl*

- Estimates of diagnostic performance for INH by Xpert MTB/XDR vs. Hain MTBDR*plus*
- Estimates of diagnostic performance for ETH by Xpert MTB/XDR vs. Hain MTBDR*plus*
- Estimates of diagnostic performance for FQ by Xpert MTB/XDR vs. Hain MTBDR*sl*
- Estimates of diagnostic performance for AMK/KAN/CAP by Xpert MTB/XDR vs. Hain MTBDR*sl*

Performance by patient HIV status:

- Estimates of diagnostic performance by HIV status (positive and negative)

Performance by patient pre-treatment status:

- Estimates of diagnostic performance by patient report of previous treatment for TB (yes and not)

Performance as reflex test to Ultra or MTB/RIF assay

- Estimates of diagnostic performance for each drug split by which test was used upfront (Ultra or MTB/RIF)

5 Baseline descriptive statistics

Descriptive statistics tables will be generated to summarize the characteristics of the participants. The number of participants included and excluded will be reported. Among the included participants, the information will be broken down by site, gender, and age group.

Results will be reported either in absolute numbers (e.g. number of subjects in a group) or summarized by mean, median, standard deviation, minimum, maximum and quartiles.

6 Planned interim analyses

Once 200 clinical samples have been tested by Xpert MTB/XDR both directly on the clinical sample and on the culture isolate, and have returned NGS results for all drugs tested, an interim analysis will be conducted. The diagnostic sensitivity and specificity of the Xpert MTB/XDR assay will be estimated against NGS for each drug evaluated, including for important sub-groups as detailed in Table 2.

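### Protocol 9.2 takes the isolate Xpert result whenever sputum and isolate disagree, so primary accuracy is that of isolate testing, not of the intended direct-from-sputum use

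*Protocol*

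**What the plan says.** Protocol 9.2 first says which samples enter the primary accuracy analyses: "All TB samples that generate both Xpert MTB/XDR and composite reference standard results will contribute to the analysis of the performance characteristics". The next sentence gives the rule at issue: "If discordances are observed between the Xpert MTB/XDR results from testing sputa and the culture isolate, results from the culture isolate will be considered".

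Other sections bear on it:

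- **Protocol 5.3.2 (Index Test)** describes the assay as detecting resistance mutations directly from sputum and continues: "In line with this intended use, clinical samples will be directly tested by the Xpert MTB/XDR assay". It adds the isolate run for comparison and to help resolve discordant results, noting that "discordance may arise as a result of infections with a mix of different strains, with only one strain being grown out in culture".
- **Protocol 7.1** says the index test is run on both materials "to ensure high Xpert MTB/XDR diagnostic performance direct from sputum and to provide a basis for comparison if any discordants are seen". On the reference standard it says: "Phenotypic MGIT DST and targeted NGS will be performed on the culture isolate for each clinical sample".
- **SAP 4.2** defines the primary outcomes without naming a specimen. For outcome 1.1: "Estimates of sensitivity and specificity of Xpert MTB/XDR will be calculated, for INH and ETH resistance detection with phenotypic DST". Outcomes 1.2 and 1.3 follow the same pattern. The per-protocol definition in SAP 3.2 does not name a specimen either.
- **SAP 4.3** places the direct result among the secondary outcomes: "Estimates of diagnostic performance for each drug split by specimen type used for Xpert MTB/XDR (sputum or culture".

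**The concern.** A rule that defers to the isolate only when the two results disagree looks like a tie-break. In effect it replaces the sputum result for every sample that has both. The primary sensitivity and specificity would then describe how the assay performs on cultured isolates. Protocol 3.2 says the clinical phase is there to determine accuracy in the settings where the test will be used, and in those settings the test is run on sputum.

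The reference standard makes this more serious. Index and reference would both be read from the same culture. Any loss of accuracy specific to sputum, and any strain lost in culture, would drop out of the primary error counts. The likely result is higher apparent accuracy. That is not certain, because a sample whose sputum result matches the reference while its isolate Xpert result does not would move the estimate down.

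These estimates are meant to inform national and global policy, so the headline figures should describe the test as it will be used. With the SAP silent, the analyst must either follow the protocol rule or choose a specimen after results are known.

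**Working it through.** **1. What the rule does.** Take a sample with a resistant (R) or sensitive (S) call on both specimens.

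| Sputum | Isolate | Agree? | Value used under 9.2 | Equals isolate? |
|---|---|---|---|---|
| R | R | yes | R | yes |
| R | S | no | S | yes |
| S | R | no | R | yes |
| S | S | yes | S | yes |

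The value used is the isolate result in 4 of 4 cases. No discordance rate is needed for this step.

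**2. How many samples it reaches.** The reference categories in Protocol 9.2.2 need a positive culture, and Protocol 6.1.2 plans a second Xpert run on cultured samples. Most analysable samples should therefore have both results.

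**3. The plan's own precision.** Table 2 uses the Wilson score interval with continuity correction. With q = 1 - p and z = 1.96:

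- Lower = [2np + z² - 1 - z√(z² - 2 - 1/n + 4p(nq + 1))] / [2(n + z²)]
- Upper = [2np + z² + 1 + z√(z² + 2 - 1/n + 4p(nq - 1))] / [2(n + z²)]

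For FQ sensitivity (n = 93, p = 0.90) this gives 81.6 to 95.0, against the printed 82 to 95. At p = 0.90, INH (n = 395) gives 86.5 to 92.7, KAN (n = 71) gives 80.0 to 95.5 and AMK/CAP (n = 34) gives 73.7 to 97.1. All match Table 2 within rounding.

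**4. Shift caused by the rule.** Among the n reference-resistant samples, let u be the number with sputum negative and isolate positive, and d the number with the reverse. Then

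sensitivity under the rule - direct sensitivity = (u - d) / n.

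The documents give no u or d, so the rates below are assumptions. For INH, n = 395:

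| u rate | d rate | Net samples | Shift (points) |
|---|---|---|---|
| 2% | 0 | 7.9 | +2 |
| 5% | 0 | 19.8 | +5 |
| 10% | 0 | 39.5 | +10 |
| 5% | 2% | 11.9 | +3 |
| 5% | 5% | 0 | 0 |
| 2% | 5% | -11.9 | -3 |

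**5. Net discordance that exceeds the planned half-width.** Half-width is half the total width printed in Table 2.

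| Drug | n | Half-width (points) | Smallest net count above it |
|---|---|---|---|
| INH | 395 | 7/2 = 3.5 | 14 (14/395 = 3.54) |
| FQ | 93 | 13/2 = 6.5 | 7 (7/93 = 7.5) |
| KAN | 71 | 16/2 = 8 | 6 (6/71 = 8.5) |
| AMK/CAP | 34 | 23/2 = 11.5 | 4 (4/34 = 11.8) |

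For AMK/CAP each net discordant sample moves sensitivity by 1/34 = 2.9 points. The printed INH width is rounded: the limits in step 3 give (92.7 - 86.5)/2 = 3.1 points, which 13/395 = 3.3 would already exceed.

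**6. Illustration for FQ (n = 93).** Assume isolate sensitivity of 90% and that every discordance is a sputum miss. The rule reports 90% (82.2 to 94.6) in each case, using Wilson without correction. Direct sensitivity would be:

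- 2% discordance: 88% (79.8 to 93.1)
- 5% discordance: 85% (76.4 to 90.9)
- 10% discordance: 80% (70.8 to 86.9)

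**7. Specificity.** The same identity holds among reference-sensitive samples. Each net discordant sample moves specificity by 1/205 = 0.5 points for INH and by 1/566 = 0.2 points for AMK/CAP.

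**The case against.** The strongest defence is that the rule compares like with like. DST, NGS and the line probe assays all come from the isolate. Protocol 5.3.2 says isolate testing will help resolve discordant results and that using one culture avoids differences in sample quality. If a mixed infection loses a strain in culture, a sputum result that found that strain would be charged as an error against a reference that never saw it. That risk is real. But explaining a discordant result does not require replacing the index result, and neither 5.3.2 nor 7.1 says to replace it. A sensitivity analysis would meet the concern.

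Other points, and what stands of each:

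- **The wording is loose.** To say the isolate result will be considered is not strictly to say it replaces the sputum result. Replacement is still the natural reading, and no other primary rule is given.
- **Section 9 is a summary and the SAP governs.** The SAP does not carry the rule, but it does not withdraw it or name a specimen. This leaves a gap and does not cure the problem.
- **Direct accuracy is still reported.** True, for each drug. The matter is which estimate is primary.
- **Sign and size are not established.** True. The assumed shifts in INH sensitivity run from -3 to +10 points and include zero.
- **Indeterminate calls are not covered.** Protocol Appendix 5 allows a valid run with an indeterminate drug result, and the documents do not say whether that counts as a discordance. The conclusion is therefore limited to samples with a resistant or sensitive call on both specimens.

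**Conclusion.** The concern holds. Under Protocol 9.2 as written, the primary sensitivity and specificity are those of isolate testing for every sample with resistant or sensitive calls on both specimens. This follows from the rule alone and rests only on reading it as replacement. It conflicts with the direct-from-sputum use stated in Protocol 5.3.2, and the SAP does not resolve the conflict.

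The numerical effect cannot be derived from the documents. An upward shift is likely because the reference comes from the same isolate, but it is not certain. Modest net discordance is enough to matter: about 3.5% of resistant samples for INH, 7.5% for FQ and 8.5% for KAN would shift sensitivity by more than the planned half-width. Because the rule decides what the primary endpoints measure, it should be corrected before database lock.

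**What to change.** Put the same statement in Protocol 9.2 and SAP 4.2, in place of the current discordance rule:

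> The primary analysis uses the Xpert MTB/XDR result from sputum, whatever the isolate result. Isolate results are used only for the secondary direct-versus-culture comparison and to describe or explain discordants, for example in a sensitivity analysis for suspected mixed infection.

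The per-protocol definition in SAP 3.2 should name the sputum result too. Both documents should also say how an indeterminate or non-determinant sputum result is handled when the isolate result is valid, so that the isolate does not re-enter the primary analysis by that route.

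The cost is a short text change in each document. Both Xpert results are already being collected, so no extra testing is needed. The headline estimates may be less favourable, and they will include some disagreements that arise because the reference is read from the isolate. The sensitivity analysis would show how many.
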